#### 10.1.5.1.4 Visit 6 (Month 4, ± 14 days)

This visit will include:

- Update contact information (address, e mail, home and cell phone number) for patient, patient's family and patient's GP/cardiologist
- ODYSSEY Outcomes card (or equivalent) mentioning patient participation in the study and site contact information:
  - Verify that patient has the card; if unsure, provide new cards to patient (and family).
  - Verify that site contact information (Investigator, Study Coordinator) provided to the patient is correct (update as necessary).
- Record of concomitant medication
- Body weight measurement

- Vital signs: SBP and DBP, heart rate
- Collection of information on suspected efficacy endpoints
- Collection of cardiovascular events of interest other than efficacy endpoints (peripheral arterial disease, venous thromboembolic events)
- Collection of adverse events
- Data collection on IMP administration and IMP compliance check by review of diary and treatment kit accountability (used and unused kits)

*NOTE: In case patient forgets to bring back diary at the visit, site should come up with an alternative solution to obtain as soon as possible information contained in patient diary in order to be able to complete IMP information in eCRF in a timely manner.*

- Check of the compliance and stability of the dose of the LMT (atorvastatin, rosuvastatin, ± other LMT)
- Urine pregnancy test (females of childbearing potential only)
- Blood sample for:
  - Lipids: TC, LDL-C, HDL-C, TG, non-HDL-C, ApoB, ApoA-1, ratio ApoB/ApoA-1, and Lp (a)
  - Liver panel (ALT, AST, ALP, and total bilirubin)
  - CPK
  - hs-CRP
  - Library samples
  - Anti- alirocumab antibodies
- EQ-5D patient questionnaire
- Double blind IMP kit dispensation as per treatment kit number provided by IVRS along with schedule reminder and the treatment administration package should be provided. The patient injection instruction manual and diary may be given, as needed
- Reminders:
  - An appointment will be given for the next study site visit
  - Remind patient to be in fasting conditions (ie, overnight, at least 8 hours fast) for next study site visit, if applicable
  - Remind patient to bring 3 items at the next study visit:
    - the diary,
    - used and unused IMP kits,
    - the ODYSSEY Outcomes card (or equivalent) containing site contact information.
  - Remind patient (and family) that, in case patient is hospitalized, they should contact the site (Investigator, Research Coordinator) as soon as possible, and not wait until the next visit.

#### 10.1.5.1.5 Visit 8 (Month 8, $\pm$ 14 days)

This visit will include:

- Update contact information (address, e mail, home and cell phone number) for patient, patient's family and patient's GP/cardiologist
- ODYSSEY Outcomes card (or equivalent) mentioning patient participation in the study and site contact information:
  - Verify that patient has the card; if unsure, provide new cards to patient (and family).
  - Verify that site contact information (Investigator, Study Coordinator) provided to the patient is correct (update as necessary).
- Record of concomitant medication
- Body weight measurement
- Vital signs: SBP and DBP, heart rate
- Collection of information on suspected efficacy endpoints
- Collection of cardiovascular events of interest other than efficacy endpoints (peripheral arterial disease, venous thromboembolic events)
- Collection of adverse events
- Data collection on IMP administration and IMP compliance check by review of diary and treatment kit accountability (used and unused kits)

*NOTE: In case patient forgets to bring back diary at the visit, site should come up with an alternative solution to obtain as soon as possible information contained in patient diary in order to be able to complete IMP information in eCRF in a timely manner.*

- Check of the compliance and stability of the dose of the LMT (atorvastatin, rosuvastatin,  $\pm$  other LMT)
- Urine pregnancy test (females of child-bearing potential only)
- Blood sample for:
  - Lipids: TC, LDL-C, HDL-C, TG, non-HDL-C
- EQ-5D patient questionnaire
- Double blind IMP kit dispensation as per treatment kit number provided by IVRS along with schedule reminder and the treatment administration package should be provided. The patient injection instruction manual and diary may be given, as needed
- Reminders:
  - An appointment will be given for the next study site visit
  - Remind patient to be in fasting conditions (ie, overnight, at least 8 hours fast) for next study site visit, if applicable

- Remind patient to bring 3 items at the next study visit:
  - the diary,
  - used and unused IMP kits,
  - the ODYSSEY Outcomes card (or equivalent) containing site contact information.
- Remind patient (and family) that, in case patient is hospitalized, they should contact the site (Investigator, Research Coordinator) as soon as possible, and not wait until the next visit.

#### 10.1.5.1.6 Visit 10 (Month 12, ± 14 days)

This visit will include:

- Update contact information (address, e mail, home and cell phone number) for patient, patient's family and patient's GP/cardiologist
- ODYSSEY Outcomes card (or equivalent) mentioning patient participation in the study and site contact information:
  - Verify that patient has the card; if unsure, provide new cards to patient (and family).
  - Verify that site contact information (Investigator, Study Coordinator) provided to the patient is correct (update as necessary).
- Record of concomitant medication
- Body weight measurement
- Physical examination including vital signs: SBP and DBP, heart rate
- Collection of information on suspected efficacy endpoints
- Collection of cardiovascular events of interest other than efficacy endpoints (peripheral arterial disease, venous thromboembolic events)
- Collection of adverse events
- Data collection on IMP administration and IMP compliance check by review of diary and treatment kit accountability (used and unused kits)

*NOTE: In case patient forgets to bring back diary at the visit, site should come up with an alternative solution to obtain as soon as possible information contained in patient diary in order to be able to complete IMP information in eCRF in a timely manner.*

- Check of the compliance and stability of the dose of the LMT (atorvastatin, rosuvastatin, ± other LMT)
- Urinalysis (at selected sites), with urine sample sent to Central Lab
- Urine pregnancy test (females of childbearing potential only)

- Blood sample for:
  - Lipids: TC, LDL-C, HDL-C, TG, non-HDL-C, ApoB, ApoA-1, ratio ApoB/ApoA-1, and Lp (a)
  - Hematology: blood cell count including hematocrit, hemoglobin, red blood cell count, reticulocyte count, white blood cell count with differential count and platelets

*NOTE: At selected sites with a longer transit time to Central Lab, a duplicate hematology sample will be collected for local assessment of reticulocyte count*

  - Chemistry: glucose, sodium, potassium, chloride, bicarbonate, calcium, phosphorous, urea nitrogen, creatinine, uric acid, LDH, total protein, albumin, and  $\gamma$ GT
  - Liver panel (ALT, AST, ALP, and total bilirubin)
  - HbA1c
  - CPK
  - hs-CRP
  - Library samples
  - Anti- alirocumab antibodies
- EQ-5D patient questionnaire
- Double-blind IMP kit dispensation as per treatment kit number provided by IVRS along with schedule reminder. The patient injection instruction manual and treatment administration package should be provided. The patient diary should be given and instructions on its completion should be reviewed
- Reminders:
  - An appointment will be given for the next study site visit
  - Remind patient to be in fasting conditions (ie, overnight, at least 8 hours fast) for next study site visit, if applicable
  - Remind patient to bring 3 items at the next study visit:
    - the diary,
    - used and unused IMP kits,
    - the ODYSSEY Outcomes card (or equivalent) containing site contact information.
  - Remind patient (and family) that, in case patient is hospitalized, they should contact the site (Investigator, Research Coordinator) as soon as possible, and not wait until the next visit.

10.1.5.1.7 Visit 12 (Month 16)/ Visit 14 (Month 20)/ Visit 18 (Month 30)/ Visit 22 (Month 42)/ Visit 26 (Month 54) ( $\pm 14$  days)

These visits will include:

- Update contact information (address, e mail, home and cell phone number) for patient, patient's family and patient's GP/cardiologist
- ODYSSEY Outcomes card (or equivalent) mentioning patient participation in the study and site contact information:
  - Verify that patient has the card; if unsure, provide new cards to patient (and family).
  - Verify that site contact information (Investigator, Study Coordinator) provided to the patient is correct (update as necessary).
- Record of concomitant medication
- Body weight measurement
- Vital signs: SBP and DBP, heart rate
- Collection of information on suspected efficacy endpoints
- Collection of cardiovascular events of interest other than efficacy endpoints (peripheral arterial disease, venous thromboembolic events)
- Collection of adverse events
- Data collection on IMP administration and IMP compliance check by review of diary and treatment kit accountability (used and unused kits)

*NOTE: In case patient forgets to bring back diary at the visit, site should come up with an alternative solution to obtain as soon as possible information contained in patient diary in order to be able to complete IMP information in eCRF in a timely manner.*

- Check of the compliance and stability of the dose of the LMT (atorvastatin, rosuvastatin,  $\pm$  other LMT)
- Urine pregnancy test (females of childbearing potential only)
- Blood sample for:
  - Lipids: TC, LDL-C, HDL-C, TG, non-HDL-C
  - Liver panel (ALT, AST, ALP, and total bilirubin)
  - CPK
- EQ-5D patient questionnaire
- Double-blind IMP kit dispensation as per treatment kit number provided by IVRS along with schedule reminder. In case an extra kit for the patient is needed, it should be done by contacting the IVRS/IWRS. The patient injection instruction manual and treatment administration package should be provided. The patient diary should be given and instructions on its completion should be reviewed

- Reminders:
  - An appointment will be given for the next study site visit
  - Remind patient to be in fasting conditions (ie, overnight, at least 8 hours fast) for next study site visit, if applicable
  - Remind patient to bring 3 items at the next study visit:
    - the diary,
    - used and unused IMP kits,
    - the ODYSSEY Outcomes card (or equivalent) containing site contact information.
  - Remind patient (and family) that, in case patient is hospitalized, they should contact the site (Investigator, Research Coordinator) as soon as possible, and not wait until the next visit.

*10.1.5.1.8 Visit 16 (Month 24)/ Visit 20 (Month 36)/ Visit 24 (Month 48)/ Visit 28 (Month 60)  
(± 14 days)*

These visits will include:

- Update contact information (address, e mail, home and cell phone number) for patient, patient's family and patient's GP/cardiologist
- ODYSSEY Outcomes card (or equivalent) mentioning patient participation in the study and site contact information:
  - Verify that patient has the card; if unsure, provide new cards to patient (and family).
  - Verify that site contact information (Investigator, Study Coordinator) provided to the patient is correct (update as necessary).
- Record of concomitant medication
- Body weight measurement
- Physical examination including vital signs: SBP and DBP, heart rate
- Collection of information on suspected efficacy endpoints
- Collection of cardiovascular events of interest other than efficacy endpoints (peripheral arterial disease, venous thromboembolic events)
- Collection of adverse events
- Data collection on IMP administration and IMP compliance check by review of diary and treatment kit accountability (used and unused kits)

*NOTE: In case patient forgets to bring back diary at the visit, site should come up with an alternative solution to obtain as soon as possible information contained in patient diary in order to be able to complete IMP information in eCRF in a timely manner.*

- Check of the compliance and stability of the dose of the LMT (atorvastatin, rosuvastatin, ± other LMT)
- Urinalysis (at selected sites), with urine sample sent to Central Lab
- Urine pregnancy test (females of childbearing potential only)
- Blood sample for:
  - Lipids: TC, LDL-C, HDL-C, TG, non-HDL-C (in addition, at Month 24 only, ApoB will be collected)
  - Hematology: blood cell count including hematocrit, hemoglobin, red blood cell count, reticulocyte count, white blood cell count with differential count and platelets

NOTE: at selected sites with a longer transit time to Central Lab, a second hematology sample will be collected for local assessment of reticulocyte count

  - Chemistry: glucose, sodium, potassium, chloride, bicarbonate, calcium, phosphorous, urea nitrogen, creatinine, uric acid, LDH, total protein, albumin, and  $\gamma$ GT
  - Liver panel (ALT, AST, ALP, and total bilirubin)
  - HbA1c
  - CPK
  - Anti- alirocumab antibodies
- EQ-5D patient questionnaire
- Double-blind IMP kit dispensation as per treatment kit number provided by IVRS along with schedule reminder. In case an extra kit for the patient is needed, it should be done by contacting the IVRS/IWRS. The patient injection instruction manual and treatment administration package should be provided. The patient diary should be given and instructions on its completion should be reviewed
- Reminders:
  - An appointment will be given for the next study site visit
  - Remind patient to be in fasting conditions (ie, overnight, at least 8 hours fast) for next study site visit, if applicable
  - Remind patient to bring 3 items at the next study visit:
    - the diary,
    - used and unused IMP kits,
    - the ODYSSEY Outcomes card (or equivalent) containing site contact information.
  - Remind patient (and family) that, in case patient is hospitalized, they should contact the site (Investigator, Research Coordinator) as soon as possible, and not wait until the next visit.

#### **10.1.5.2 Contacts (phone calls, text messages or contacts via internet) from randomization**

Contacts should be scheduled in between on-sites visits as follows: Visit 7 (Month 6)/ Visit 9 (Month 10)/ Visit 11 (Month 14)/ Visit 13 (Month 18)/ Visit 15 (Month 22)/ Visit 17 (Month 27)/ Visit 19 (Month 33)/ Visit 21 (Month 39)/ Visit 23 (Month 45)/ Visit 25 (Month 51)/ Visit 27 (Month 57)/ Visit 29 (Month 62).

Although flexibility is allowed in the timing of phone call in between the on-site/clinic visits, it should be scheduled with the goal of maintaining a contact with the patient about every 2 months during first 24 months, and about every 3 months thereafter. Having no phone or email contact with a patient for a prolonged period (>4 months) should be avoided as much as possible. Some additional instructions for scheduling phone call may be provided at time of interim analysis.

This contact will include:

- Update contact information (address, e mail, home and cell phone number) for patient, patient's family and patient's GP/cardiologist
- Review compliance with background LMT (including statin, ezetimibe)
- Collection of information on IMP administration (and remind patient to complete diary)
- Collection of information on suspected efficacy endpoints (and remind patient to call site in case of hospitalization and not wait until next visit)
- Reminders: as applicable for IMP administration schedule, timing of next visit, fasting conditions for next lab assessment, to bring the diary and used and unused kits at the next study site visit

In addition to the contacts detailed above, a SMS/text messaging vendor (EXCO InTouch) has been engaged to send appointment and injection reminders to any patient who wishes to and is able to receive them. This service is optional and each study site will have the opportunity to participate or refuse as per their policies.

These contacts will conform to privacy regulations at each site.

#### **10.1.5.3 Early end of treatment visit – Visit 70**

For patients who will have prematurely permanently discontinued IMP (see [Section 10.3.2](#) for more details on when to consider that a patient has permanently discontinued treatment), an end of treatment visit called Visit 70 (early end of treatment visit) will be performed as soon as practically possible (within 1 month) after IMP discontinuation is considered permanent by the Investigator. Assessments done at this visit will be similar to those planned for the study completers at the final visit (Visit 30, Month 64) (see [Section 1.2](#)).

In addition:

- Update contact information (address, email, home and cell phone number) for patient, patient's family, and patient's GP/cardiologist
- ODYSSEY Outcomes card (or equivalent) mentioning patient participation in the study and site contact information:
  - Verify that patient has the card; if unsure, provide new cards to patient (and family).
  - Verify that site contact information (Investigator, Study Coordinator) provided to the patient is correct (update as necessary).

Then those patients must continue to remain in the study and will be strongly encouraged to complete all the remaining study visits as originally scheduled (as described in [Section 1.2](#)), until the common study end date (ie, final visit, Visit 30, Month 64). Complete usual study assessments (with the exception of IMP administration and its associated procedures) will be performed for 6 months following V70. Thereafter, study assessments are reduced (see [Section 10.3.4](#) for more details). Patients who will not be able to attend any particular study visit will be invited to attend a subsequent visit.

Finally, the Investigator will make every effort to contact participants who are lost to follow-up. Attempts to contact such participants must be documented in the participant's records.

#### **10.1.5.4 Common study end date visit (Final Visit) – Visit 30 (~Month 64, between CSED and CSED + 30 days)**

This final CSED visit should be scheduled and be performed on or shortly after the actual occurrence of the CSED (see also [Section 6.2.2](#)). CSED is scheduled to occur at around Month 64, and will be announced by the sponsor in advance in order for sites to be able to plan this final visit.

This final CSED visit (Visit 30, Month 64):

- should be a clinic visit,
- should be performed for all randomized patients regardless of the patient status (still receiving IMP or having prematurely discontinued IMP permanently),
- however there are some differences on how to plan the visit (and last IMP injection, when applicable) and in assessments to be performed at that final visit, depending on patient status.

For patients still receiving IMP (study completers), both CSED visit and last IMP injection should be determined taking into account the following:

- CSED visit should take place between CSED and CSED + 30 days
- CSED visit should occur 14 days ( $\pm 3$  days) after last IMP injection
- Site has clearly communicated and agreed in advance with patient (and family) on date of last IMP injection and date of CSED visit

- In order to ensure compliance with these critical final study procedures, sites should:
  - contact patients a few days prior to the agreed-upon date of last IMP injection,
  - remind patient about the final IMP injection and final CSED visit, and
  - ask patient to return to the investigational site in the morning preferably in fasting condition (ie, overnight, at least 8 hours fast) and to bring the used and unused kits and the diary.

Assessments to be performed at the CSED visit for study completers are described in [Section 10.1.5.4.1](#).

For patients who had previously permanently discontinued IMP:

- CSED visit should take place between CSED and CSED + 30 days.
- Site has communicated and agreed in advance with patient (and family) on date of CSED visit.
- In order to ensure compliance with these critical final study procedures, sites should:
  - contact patients a few days prior to the final CSED visit, and
  - ask patient to return to the investigational site in the morning preferably in fasting condition (ie, overnight, at least 8 hours fast).
  - If IMP permanent discontinuation occurred after the prior most recent clinic visit and/or if patient still has IMP kits at home, patient should bring the used and unused kits and the diary.

Assessments to be performed at the CSED visit for patients who had permanently discontinued IMP are described in [Section 10.1.5.4.2](#).

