- g Hematology includes: complete blood cell count (CBC) including hematocrit, hemoglobin, red blood cell count, reticulocyte count, white blood cell count with differential count, and platelets (Note: reticulocyte not done at V1). Chemistry includes: glucose, sodium, potassium, chloride, bicarbonate, calcium, phosphorous, urea nitrogen, creatinine, uric acid, LDH, total protein, albumin, and  $\gamma$ GT.
- h Liver panel: ALT, AST, alkaline phosphatase (ALP), and total bilirubin. Hepatitis C antibody: In case of positive hepatitis C antibody test, a blood sample will be collected at a subsequent visit and sent to Covance Central Lab for further confirmatory testing
- i Pregnancy tests (serum, urine) in Women of Child Bearing Potential (WOCBP) only. Urinalysis to be performed only at selected sites (see [Section 10](#)).
- j Library samples should be collected, as permitted by local regulatory policies. They may be stored for up to 10 years or as permitted by local regulatory policies, whichever is shorter, for exploratory research of PCSK9 levels, PCSK9 function, effect(s) of PCSK9 inhibition with a monoclonal antibody, lipoprotein sub-fraction, inflammation, and cardiovascular risk markers (eg, lipoprotein-associated phospholipase A2).
- k If blood sample not collected at randomization, could be collected at any time during the study.
- l EQ-5D patient questionnaire will only be administered in patients still on treatment, for prematurely (permanently) discontinued patients the last administration will be done at the early end of treatment visit.
- m Common study end date (CSED) will occur 24 months after the closing of randomization ex-China or after the target number of events (1613) is reached whichever comes last. A final clinic visit V30 (CSED visit, Month 64) should be completed within 30 days of CSED for all randomized patients regardless of the compliance with study treatment (see [Section 10.1.5.1.4](#)). Reduced assessments in 'Prematurely discontinued patients' column apply only if V30 occurs more than 6 months after V70 (see [Section 10.3.4](#)).

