- n For patients who prematurely discontinue blinded study treatment (IMP): as a general rule, any IMP treatment discontinuation should be initially considered temporary, and Investigator should make best effort to resume IMP treatment as early as practically possible, after several weeks or months (pending there are no safety concerns), and perform all study visits and assessments as usual. Investigator is strongly encouraged to discuss with monitoring team before considering any treatment discontinuation as permanent. A discussion with National Coordinator may occur regarding other possible options. If and when a treatment discontinuation is considered 'permanent', an extra visit (early end of treatment visit V70) should be performed as soon as practically possible (within 1 month) after IMP discontinuation is considered permanent by Investigator. Such patients (with premature permanent treatment discontinuation) must continue to remain in the study and should return for all study visits until the common study end date (final visit V30). Complete usual study assessments should be performed for 6 months following V70. Thereafter, assessments are reduced to collection of suspected efficacy endpoints, cardiovascular events of interest other than efficacy endpoints (peripheral arterial disease, venous thromboembolic events – see [Section 9.3.7](#)), related and/or serious AEs, selected concomitant medications (statins, ezetimibe) and selected labs (anti-alirocumab antibodies, lipid panel, ApoB, HbA1c) (See [Section 10.3.4](#)).

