## 9.2 SAFETY ENDPOINT(S):

### Observation period

The observation of safety data will be as follows:

- PRE-TREATMENT period: The PRE-TREATMENT observation period is defined from the signed informed consent up to the first dose of double-blind IMP injection
- Treatment Emergent Adverse Event (TEAE) period: The TEAE observation period is defined as the time from the first dose of double-blind IMP injection to the last dose of IMP injection + 70 days (10 weeks) as residual effect of treatment is expected until 10 weeks after the stop of double-blind IMP
- POST-TREATMENT period: The POST-TREATMENT observation period is defined as the time starting the day after the end of the TEAE period up to the end of the study

Rationale for TEAE period definition is detailed in [Section 4](#).

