#### 10.1.5.4.2 Final Visit - Visit 30 for prematurely discontinued patients

This visit will include:

- Collection of information on suspected efficacy endpoints
- Collection of cardiovascular events of interest other than efficacy endpoints (peripheral arterial disease, venous thromboembolic events)
- Collection of related and/or serious AEs
- Selected concomitant medications (statin, ezetimibe)
- Blood sample for
  - Lipids: TC, LDL-C, HDL-C, TG, non-HDL-C, ApoB
  - HbA1c
  - Anti-alirocumab antibodies
- IVRS/IWRS contact for notification of the date of this final visit

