### 10.3.4 Handling of patients after permanent treatment discontinuation

Patients in whom IMP treatment discontinuation is considered permanent by Investigator should come for an extra visit (early end-of-treatment visit V70) as soon as practically possible (within 1 month) after IMP discontinuation is considered permanent by Investigator. V70 is similar to the common end of study visit (Visit 30, Month 64) for study treatment completers, and should include similar procedures.

Such patients must continue to remain in the study and will be strongly encouraged to complete all the remaining study visits as originally scheduled in [Section 1.2](#), until the common study end-date visit. Therefore, a contact should be maintained with these patients every 2 to 3 months (as per study assessments), and a clinic visit performed every 4 to 6 months until the common study end-date visit (V30).

- Over the 6 months following V70, all assessments (other than IMP administration and its associated procedures) should be performed as originally planned. These include but are not limited to collection of suspected efficacy endpoints, AE/AESI/SAE, concomitant medications, hematology and chemistry labs, lipid labs and anti- alirocumab antibodies.
- From 6 months post V70 until common study end date visit (V30), assessment at visits are simplified and will include updating patient contact information (as well as patients' family and patient's GP/cardiologist) and the collection of:
  - suspected efficacy endpoints
  - cardiovascular events of interest other than efficacy endpoints (peripheral arterial disease and venous thromboembolic events)
  - related and/or serious AEs
  - selected concomitant medications (statins, ezetimibe)
  - selected labs:
    - anti alirocumab antibodies, lipid panel and HbA1c: annually (at M12, M24, M36, M48, M60) and at common study end-date
    - ApoB at month 24 and at common study end-date.

Previously observed AEs/AESIs/SAEs that had not resolved should be followed-up until an outcome (e.g. resolution, stabilization) has been determined.

- In case of difficulty to comply with the 4 to 6-month clinic visit periodicity in patients who discontinued treatment early, every effort should be made to have an actual clinic visit at least annually (with periodic phone/internet contacts every 3 months in between) and a final visit V30. During that annual visit and at V30, selected blood samples as described above should be collected.

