#### 10.4.4 General guidelines for reporting adverse events

- AEs are to be recorded in corresponding screen(s) included in the eCRF.
- The reporting requirement of AEs depends on patient status (study completer or patient who had premature permanent discontinuation of IMP)
  - In patients who receive IMP until the end of the study (study completer), all AEs, regardless of seriousness or relationship to IMP/NIMP, spanning from the signature of the informed consent form until the CSED visit are to be recorded in the eCRF. Patients who experience a new or ongoing related or serious AE or a new or ongoing AESI (see [Section 10.4.2](#)) at the CSED visit should be followed beyond the CSED visit until resolution, stabilization, or death (whichever comes first) and related data will be collected (see [Section 10.1.5.4.1](#)).
  - In patients who have permanent premature IMP discontinuation:
    - All AEs, regardless of seriousness or relationship to IMP/NIMP, spanning from the signature of the informed consent form until 6 months following V70 (end of treatment visit) are to be recorded in the eCRF.
    - From 6 months following V70 until the CSED visit, related and/or serious AEs should be recorded in the eCRF.

***NOTE:** Reporting requirement for suspected efficacy endpoints is the same regardless of patient status (study completers or patients who had premature permanent discontinuation of IMP); suspected efficacy endpoints should be reported in all randomized patients until the end of the study (CSED).*

- Whenever possible, diagnosis or single syndrome should be reported instead of symptoms. The Investigator should specify the date of onset, intensity, action taken with respect to IMP, corrective treatment/therapy given, additional investigations performed, outcome, and his/her opinion as to whether there is a reasonable possibility that the AE was caused by the IMP.
- When treatment is prematurely discontinued, the patient will be maintained in the study and the patient's observations will continue until the common study end date visit (see [Section 10.3.4](#)).
- Laboratory, vital signs or ECG abnormalities are to be recorded as AEs only if:
  - Symptomatic and/or
  - Requiring either corrective treatment or consultation, and/or
  - Leading to IMP discontinuation or modification of dosing (with exception of LDL-C levels which may lead to IMP dosing modification, but in a blinded manner), and/or

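### The final-visit section gives every patient who has permanently stopped study drug the reduced assessment list, while the flow chart and four other passages require full assessments or all-AE recording for 6 months after V70

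*Protocol*

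**What the plan says.** Protocol Section 10.1.5.4 divides patients at V30 into those still receiving IMP and those who had permanently discontinued it. For the second group it says: "Assessments to be performed at the CSED visit for patients who had permanently discontinued IMP are described in" Section 10.1.5.4.2. How long ago the patient stopped plays no part. The AE item in that list reads "Collection of related and/or serious AEs". The list otherwise covers efficacy endpoints, cardiovascular events of interest, statin and ezetimibe use, lipids with ApoB, HbA1c and antibodies. It contains no hematology, chemistry, liver panel, CPK or ECG.

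Five other places set a 6-month rule:

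- Flow chart footnote m (Section 1.2.1): "Reduced assessments in 'Prematurely discontinued patients' column apply only if V30 occurs more than 6 months after V70".
- Flow chart footnote n: "Complete usual study assessments should be performed for 6 months following V70".
- Section 10.1.5.3: "Complete usual study assessments (with the exception of IMP administration and its associated procedures) will be performed for 6 months following V70".
- Section 10.3.4: "Over the 6 months following V70, all assessments (other than IMP administration and its associated procedures) should be performed as originally planned".
- Section 10.4.4, on what is recorded after permanent discontinuation: "All AEs, regardless of seriousness or relationship to IMP/NIMP, spanning from the signature of the informed consent form until 6 months following V70".

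Section 10.1.1 goes further and has all AEs collected until V30 for everyone.

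**The concern.** A patient whose V70 was 6 months or less before V30 is under two incompatible instructions at the same visit. Sections 10.1.5.4 and 10.1.5.4.2 are the text a site is likely to work from when it prepares that visit. Footnote m holds the limiting condition, but for the final visit it refers to Section 10.1.5.1.4, which is the Month 4 visit. A reader who follows it does not arrive at the conflicting list.

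Safety ascertainment is what is at stake. The protocol's TEAE period runs to "last dose of IMP injection + 70 days (10 weeks"), and the SAP uses the same limit. SAP Section 3.4.5.1 censors patients without an event at the end of that period, so they count as at risk whether or not anyone asked about AEs. SAP Section 3.4.5 derives laboratory abnormalities (PCSAs) from all evaluations in the period, and Section 3.1.4.1 identifies the ALT event of special interest from laboratory data. Without a liver panel it cannot be detected at that visit. Every patient's V30 falls between the CSED and 30 days after it, and no later scheduled visit would correct an omission.

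**Working it through.** The plan states no figure on this point, so there is none to reproduce. The check compares the passages, then does day arithmetic, then sizes the exposed group under an assumption.

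**1. Which rule applies to whom**

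| Patient at V30 | 10.1.5.4 and 10.1.5.4.2 | Footnotes m and n, 10.1.5.3, 10.3.4, 10.4.4 |
|---|---|---|
| Stopped, V30 more than 6 months after V70 | Reduced list | Reduced list |
| Stopped, V30 6 months or less after V70 | Reduced list | Full assessments except IMP procedures; all AEs |
| Stopped, V30 is the first visit after stopping | Reduced list | Footnote m's test for the reduced list is not met |

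The rules agree only in the first row. The third row is a real possibility: 10.1.5.4 itself foresees patients who stopped after their most recent clinic visit, when it asks them to bring back kits and diary.

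**2. How much of the gap is treatment-emergent**

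Six months is 6 × 30.4375 = 182.6 days, using the SAP's month length. The TEAE window is 70 days from the last dose. V70 is done within 1 month of the decision that stopping is permanent. That decision can come well after the last dose, because Section 10.3 has any stop treated as temporary at first. Treatment-emergent days still open after V70 = max(0, 70 − days from last dose to V70):

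| Last dose to V70 (days) | 0 | 14 | 30 | 44 | 60 | 70 or more |
|---|---|---|---|---|---|---|
| TEAE days left after V70 | 70 | 56 | 40 | 26 | 10 | 0 |

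Non-serious, unrelated AEs with onset in those days are the treatment-emergent AE data at risk. They can be missed even if V30 comes after day 70. Clinic visits are 6 months apart after year 2, and the phone-contact lists in Sections 1.2.2 and 10.1.5.2 contain no AE collection, so V30 may be the only clinic visit after V70. The V30 laboratory tests are treatment-emergent only if V30 itself falls within 70 days of the last dose. Everything else in the 6-month window is post-treatment data.

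**3. How many patients meet the conflict**

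The documents give no discontinuation rate. Assume a permanent stopping rate h of 2%, 5% or 8% per year and 18,600 patients:

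- Last 6 months: 18,600 × h × 0.5 = 186, 465 or 744.
- Last 70 days: 18,600 × h × 70/365.25 = 71, 178 or 285.

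This treats all 18,600 as still on drug near the end and so leans high. With the planned accrual table scaled to 18,000 patients, CSED at month 64 and a constant hazard, 3% and 6% per year give 246 and 448 in the last 6 months. The simple formula gives 18,600 × 0.03 × 0.5 = 279 and 18,600 × 0.06 × 0.5 = 558. The counts are also approximate because the 6-month rule runs from V70, not from the last injection.

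**The case against.** The best reply is that the protocol has settled the matter. Footnote m is the specific rule for this visit and this flow-chart column, the section just before 10.1.5.4 repeats the 6-month rule, and Section 10.4.4 governs AE recording. A site would have to follow 10.1.5.4.2 against all of these before anything was missed. That stands: the loss is conditional on which text a site uses, and nothing in the documents shows that sites would divide. It does not remove the contradiction, because the visit section has no such condition and footnote m's cross-reference leads elsewhere.

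A reader might infer that late stoppers lose their end-of-treatment safety laboratory set. The documents do not support that in general. Sections 10.1.5.3 and 10.3.4 require V70 with assessments similar to the completers' final visit, and the flow chart marks AE recording, ECG, hematology, chemistry, CPK and liver panel for it. The inference would fit only a patient for whom no separate V70 took place.

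A reader might also infer that treatment-emergent data are lost across the whole 6 months, or that the affected group stops mainly because of adverse events. The first fails on the day arithmetic above. On the second, the documents give neither reasons for stopping nor their frequency.

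**Conclusion.** The passages contradict each other and should be reconciled. At sites that follow 10.1.5.4.2, for patients with V30 within 6 months of V70, two things could be missed:

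- non-serious, unrelated AEs arising after V70, which are treatment-emergent only up to 70 days after the last dose;
- the V30 safety laboratory tests, which are treatment-emergent only if V30 falls within those 70 days.

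On an assumed 2% to 8% stopping per year, the exposed group is roughly 190 to 740 patients for the 6-month window and 70 to 285 for the 70-day window. These figures count patients under conflicting instructions; they do not measure lost events.

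Missed events would lower TEAE rates somewhat, since the person-time stays in the denominator. Sites are blinded, so a bias between arms would need late stopping to differ by arm, and nothing in the documents indicates that it does. Related and serious AEs and efficacy endpoints are collected under both lists, so the primary analysis is unaffected. This is an inconsistency in the safety-collection text that is worth correcting; it does not undermine the design.

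**What to change.** Reconcile the passages by applying the protocol's own condition:

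1. In 10.1.5.4 and at the head of 10.1.5.4.2, state that the reduced list applies only if V30 is more than 6 months after V70.
2. State that all other permanently discontinued patients, including any for whom V30 is the first visit after stopping, have the usual V30 assessments and all-AE recording. Except IMP procedures, but keep the accountability that 10.1.5.4 already asks for where kits remain. Except EQ-5D once V70 has been done: the completers' list in 10.1.5.4.1 includes it, whereas footnote l and Section 9.3.5 end it at V70, so a bare reference to that list would create a new conflict.
3. Correct footnote m's cross-reference from 10.1.5.1.4 to 10.1.5.4.

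The cost is a few sentences and a reminder to sites before the CSED. The flow chart and Section 10.3.4 already require these assessments, so no new procedure is added, and no sample size, power or alpha figure changes.
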